Multiple studies have demonstrated that completing therapy with an oral agent following an initial duration of parenteral administration compared with parenteral therapy alone results in equivalent outcomes for treating musculoskeletal infections.(14, 15) In other studies, a high rate of complications was noted in children being treated for acute osteomyelitis who have parenteral antibiotics administered through a peripherally placed central catheter.(16) Thus, switching to oral administration of appropriate antibiotics to complete treatment of acute osteomyelitis is an important option for many, if not, most patients. The recommended duration of total treatment for acute osteomyelitis is at least three weeks depending on the clinical response of the patient.

4.2.Ceftaroline Fosamil

Ceftaroline is a fifth generation cephalosporin with excellent in vitro activity against *S. aureus* isolates including methicillin resistant strains.(17) Ceftaroline is approved by the United States Food and Drug Administration for treatment of skin and soft tissue infections caused by MRSA in adults based on two large randomized trials. (18, 19) In a rabbit model of MRSA osteomyelitis, ceftaroline and linezolid were significantly better than vancomycin in decreasing colony forming units in bone and joint fluid.(20) In seven of ten adult patients with deep seated MRSA infections, including osteomyelitis and septic arthritis in two patients each, ceftaroline treatment resulted in a microbiologic cure.(21) Clinical trials of ceftaroline in children are being conducted and the role of ceftaroline in treating MRSA osteomyelitis will need to be determined.

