5.2. Secondary Objectives

- Evaluate efficacy of ceftaroline in pediatric subjects with acute hematogenous osteomyelitis at the end of IV therapy, at the end of total therapy (anticipated to be at 4 to 6 weeks after enrollment), and at one year after enrollment.
- Evaluate clearance of *S. aureus* bacteremia if blood cultures initially positive.
- Assess proportion of patients with plasma levels of ceftaroline that exceed 1 µg/mL for over 60% of a dosing interval.

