6.3. Expected Duration of Subject Participation

The duration of subject participation from signing the informed consent form will be up to 14 months (includes screening period (1 Day), study IV drug administration (approximately 5-14 Days), Standard of Care Oral Drug Administration (4-5 weeks) (**the total maximum treatment period is typically 6 weeks**), and a follow-up visit 12 months after the last dose of study drug). Baseline assessments for study eligibility will occur within 24 hours before the first dose of study drug. A minimum of 2 days (48 hours) of study drug administration is required.

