9.3. Study Days 2-14

The total duration of IV ceftaroline is dependent on the subject's response to therapy but 5-14 days is anticipated in most subjects. If the subject is able to switch to oral drug before Day 15, the procedures outlined for Day 15 (EOIV) should be performed. The rest of the visit schedule will be followed as described in Table 2.1.

- Study Drug Administration:

IV ceftaroline fosamil **15 mg/kg** (or 600 mg if > 40 kg) infused over 120 (\pm 10) minutes q8h (\pm 1 hour) for children **2 years of age – 17 years** of age (inclusive).

IV ceftaroline fosamil **10 mg/kg** infused over 120 (\pm 10) minutes q 8h (\pm 1 hour) for children from **1 year of age to < 2 years** (inclusive) until the subject transitions to oral therapy.

- Clinical Assessments – any time during study day (assessments will be performed for research unless they are already being performed per standard of care; exceptions are indicated):
 - Record concomitant medications (Section 8.3). For subjects who are being breast fed, record all medications taken by the lactating mother.
 - Record resting vital signs (pulse, blood pressure, and respiratory rate), and highest postdose temperature measured.
 - Record adjunctive therapeutic procedures (eg, surgeries).
 - Record standard of care radiology results.
 - Evaluate and record physical findings of hematogenous SA osteomyelitis (eg, warmth, tenderness, swelling, erythema, and movement of the infected extremity). Most of the subjects are expected to have surgical incision and drainage procedures and thus assessing the extremity for swelling, erythema, warmth and tenderness may not be possible because of drains in place and large surgical dressings that cannot be removed. The degree of the subject's ability to ambulate will be assessed if the osteomyelitis is in the lower extremity- ie. walks unaided, able to bear weight, can walk aid using a walker, etc. The use of upper and lower extremities will be assessed in terms of movement and range of motion.
 - Identify, assess, and record any new or ongoing AEs or SAEs
- Laboratory Assessments – any time during the study period if clinically indicated (assessments will be performed for research unless they are already being performed per standard of care; exceptions are indicated):
 - Collect CRP and ESR lab results, if clinically indicated.
 - Collect CBC with differential, BUN, and Creatinine, lab results, if clinically indicated.

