9.5. Week 2, Week 4, and Week 6 After Discharge

- PO drug administration:
 - o PO clindamycin 13 mg/kg/dose q8h in subjects with proven MRSA infection due to clindamycin susceptible MRSA or when no pathogen is isolated.
OR
 - o PO cephalexin 25 to 33 mg/kg/dose q 8 hours in subjects with proven MSSA infection.
OR
 - o PO linezolid 600 mg q12h (Children > 12 years old) or 10 mg/kg q8h (children <=12 years old) in subjects with clindamycin-resistant MRSA pathogens.

Clinical Assessments - any time during study day (assessments will be performed for research unless they are already being performed per standard of care; exceptions are indicated):

- o Obtain an interval medical and surgical history focusing on the involved extremity, including history

of surgical procedures for complications of hematogenous SA osteomyelitis (eg, drainage of the bone) and all active conditions from the following categories.

- o Record concomitant medications (Section 8.3). For subjects who are being breast fed, record all medications taken by the lactating mother.
- o Record vital signs: resting pulse, blood pressure, and respiratory rate.
- o Record adjunctive therapeutic procedures (eg, surgeries).
- o Record standard of care radiology results.
- o Evaluate and record physical findings of hematogenous SA osteomyelitis (eg, warmth, tenderness, swelling, erythema, and movement of the infected extremity). Most of the subjects are expected to have surgical incision and drainage procedures and thus assessing the extremity for swelling, erythema, warmth and tenderness may not be possible because of drains in place and large surgical dressings that cannot be removed. The degree of the subject's ability to ambulate will be assessed if the osteomyelitis is in the lower extremity- ie. walks unaided, able to bear weight, can walk aid using a walker, etc. The use of upper and lower extremities will be assessed in terms of movement and range of motion.
- o Assess clinical outcome (site of infection has complete resolution of pain, swelling and warmth and the patient is able to use the affected extremity normally and is back to normal activities).
- o Identify, assess, and record any new or ongoing AEs or SAEs.

Laboratory Assessments - any time during study day, but before starting PO study drug, if applicable (assessments will be performed for research unless they are already being performed per standard of care; exceptions are indicated):

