- o Collect CRP and ESR lab results, if clinically indicated for standard of care.
- o If clinically indicated, estimate CrCl using the updated Schwartz "bedside" formula (Schwartz et al, 2009).

9.6. End of Antibiotic Therapy (EOT)/Week 4/ OR Week 6

Note that EOT visit and assessments may occur at the Week 4 visit or the Week 6 visit. If the EOT visit occurs on the same day as the Week 4 or Week 6 visit, only the EOT visit will be recorded in CTMS.

- If applicable, as PO drug may or may not be given on the same calendar day as EOT assessments, administer PO drug as described in Section 9.2.
- Clinical Assessments - any time during visit (assessments will be performed for research unless they are already being performed per standard of care; exceptions are indicated):

- o Record concomitant medications (Section 8.3). For subjects who are being breast fed, record all medications taken by the lactating mother.
- o Record height and weight.
- o Record vital signs: resting pulse, blood pressure, respiratory rate and temperature.
- o Record adjunctive therapeutic procedures (eg, surgeries), if performed.
- o Record standard of care radiology results.
- o Evaluate and record physical findings of hematogenous SA osteomyelitis (eg, warmth, tenderness, swelling, erythema, and movement of the infected extremity). The degree of the subject's ability to ambulate will be assessed if the osteomyelitis is in the lower extremity- ie. walks unaided, able to bear weight, can walk aid using a walker, etc. The use of upper and lower extremities will be assessed in terms of movement and range of motion.
- o Assess clinical outcome (site of infection has complete resolution of pain, swelling and warmth and the patient is able to use the affected extremity normally and is back to normal activities).
- o Identify, assess, and record any new or ongoing AEs or SAEs

- Laboratory Assessments (Local Laboratory) - any time during visit, Collect CRP and ESR lab results, if clinically indicated for standard of care.
 - o Obtain urine sample for urine pregnancy (for a female who has reached menarche).
 - o If clinically indicated, estimate CrCl using the updated Schwartz "bedside" formula (Schwartz et al, 2009).

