12.5. Efficacy Analysis

- Clinical response by subject and by baseline pathogen at the conclusion of IV ceftaroline.
- Clinical outcome at the completion of total therapy (IV plus oral)
- Clinical outcome at one year after enrollment into study long-term follow-up.

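### End-of-therapy success in 12.5 is scored at a time that can depend on response, and no analysis of clinical outcome at a common early time is planned beside it

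*Combined protocol and SAP*

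**What the plan says.** Section 12.5 (Efficacy Analysis) names three times: the conclusion of IV ceftaroline, "Clinical outcome at the completion of total therapy (IV plus oral", and "Clinical outcome at one year after enrollment into study long-term follow-up". No study day or window is attached to the second.

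Other sections describe when that second time falls:

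- Section 5.2 sets the objective "at the end of total therapy (anticipated to be at 4 to 6 weeks after enrollment", which is an expectation and not a fixed day.
- Section 6.3 adds that "the total maximum treatment period is typically 6 weeks".
- Section 9.6: "Note that EOT visit and assessments may occur at the Week 4 visit or the Week 6 visit". When the visits coincide, only EOT is entered in the database.
- The background (4.1) says: "The recommended duration of total treatment for acute osteomyelitis is at least three weeks depending on the clinical response of the patient". Section 9.3 says of the IV part: "The total duration of IV ceftaroline is dependent on the subject's response to therapy".

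Section 9.5 has staff make the same judgement at the Week 2, 4 and 6 visits: "Assess clinical outcome (site of infection has complete resolution of pain, swelling and warmth", together with normal use of the limb and return to normal activities. Section 12 contains no analysis for those visits. In Table 1.1 the clinical-outcome row, as it reads, is marked at EOIV, EOT and follow-up but not at Weeks 2, 4 and 6.

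**The concern.** The moment of scoring can depend on what is being scored. A child whose limb is still swollen at four weeks can stay on oral antibiotics and be assessed later, perhaps after it has settled. Nothing in the plan counts the extension. The failure rule in 7.8.2 applies when treatment is discontinued for insufficient effect, and a child whose course is merely prolonged has not been discontinued.

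The EOT proportion then pools children assessed at different times since enrollment, with the later assessments more likely in slow responders. It can be higher than the proportion resolved at any one common time in the 4 to 6 week range that the objective has in mind. In a single-arm trial a reader has no comparator with which to judge the effect, and section 12 plans no summary of antibiotic duration that would reveal it.

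**Working it through.** **1. The plan's own figure.** Section 6.2 gives 18 subjects from A'Hern's design with p0 = 0.50, p1 = 0.80, alpha 0.05 and power 80%. For each n, take the smallest r with P(X ≥ r | 0.50) ≤ 0.05, then find the smallest n with P(X ≥ r | 0.80) ≥ 0.80:

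- n = 16, r = 12: power 0.798
- n = 17, r = 13: power 0.758
- n = 18, r = 13: one-sided alpha 0.0481, power 0.867

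So 18 reproduces with a one-sided alpha. Section 6.2 does not say which endpoint π is.

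**2. What one child is worth.** 1/18 = 5.6 percentage points.

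**3. Illustration of direction and size (assumed counts).** Suppose k of 18 children are unresolved at a common visit and resolve on further antibiotics before EOT is scored, and all others are resolved at both times. Exact (Clopper-Pearson) 95% limits for x/n are the 2.5% point of Beta(x, n−x+1) and the 97.5% point of Beta(x+1, n−x). For 18/18 the lower limit is 0.025^(1/18) = 0.815.

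| k | Common visit | EOT | Difference |
|---|---|---|---|
| 0 | 18/18 = 100% (81% to 100%) | 18/18 = 100% | 0 |
| 2 | 16/18 = 89% (65% to 99%) | 18/18 = 100% | 2/18 = 11 points |
| 4 | 14/18 = 78% (52% to 94%) | 18/18 = 100% | 4/18 = 22 points |

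EOT is 100% in every row only because the example makes it so.

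The opposite case also exists. If two children stop at Week 4 with residual signs that clear by Week 6, EOT is 16/18 = 89% and Week 6 is 18/18 = 100%.

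**4. Are the 9.5 visits a common time?** The heading of 9.5 counts them from discharge. IV treatment is expected to last 5 to 14 days, and 9.4 expects less than 24 hours in hospital after the oral switch, so discharge falls roughly on days 5 to 15. Counted from the start of treatment:

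- Week 2 visit: 5 + 14 = 19 to 15 + 14 = 29 days, or 2.7 to 4.1 weeks
- Week 4 visit: 5 + 28 = 33 to 15 + 28 = 43 days, or 4.7 to 6.1 weeks
- Week 6 visit: 5 + 42 = 47 to 15 + 42 = 57 days, or 6.7 to 8.1 weeks

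The oral-switch criteria in 8.4 are response criteria, so discharge depends on response too. But footnote 14 of Table 1.1 holds the Week 2 visit only if the child was discharged before Week 2, which makes sense only if weeks run from enrollment or first dose. The two readings conflict.

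**5. If π were the EOT outcome (the documents do not say so).** Assume a common-time rate of 0.50, with a share f of unresolved children resolving during extra treatment. The EOT rate is 0.50 + 0.50f:

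- f = 0: rate 0.50, P(≥ 13/18) = 0.048
- f = 0.1: rate 0.55, P = 0.108
- f = 0.2: rate 0.60, P = 0.209
- f = 0.4: rate 0.70, P = 0.534

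**The case against.** The best defence is that the trial expects a bounded course. Section 12.3 speaks of 4 to 6 weeks of total treatment and 6.3 of 4 to 5 weeks of oral drug. The sentence in 4.1 is background on recommended practice, not a rule in this trial for extending oral therapy. There are safeguards too: children who need IV treatment after the oral switch leave the study, withdrawn children not already failures are indeterminate rather than successes, 6.1 tracks relapse and pathologic fracture, and 12.5 has a one-year outcome. EOT outcome is secondary in an 18-child safety trial and is not listed in 12.3.

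Much of this stands, and it limits the consequence. It does not supply a fixed assessment time: the 4 to 6 weeks are anticipated, six weeks is only typical, and no section overrides the dependence on response. The one-year outcome answers a different question, and 9.7 schedules that visit from the last dose although 12.5 counts from enrollment. The absence of EOT from 12.3 is an inconsistency with 5.2, 6.1 and 12.5, not a reason to leave its timing open.

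A second objection is that the 9.5 visits, if counted from discharge, have the same weakness. That is right (step 4), and any added analysis must first state what its weeks are counted from.

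A reader might also infer that the Week 4 and Week 6 assessments are never analysed. Section 9.6 does not support this: where one of them is also EOT, it is analysed under that name. Only the assessments that do not coincide go unused.

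**Conclusion.** The point holds as a gap in the efficacy analysis. EOT success is scored at a time that is not fixed and can depend on response, and no outcome at a common early time is planned although 9.5 collects the data. The EOT proportion can therefore be inflated relative to success at a common time. The amount cannot be known from the documents. On assumed counts of two or four late resolvers it would be 11 or 22 points.

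Three stronger readings are tempting and not supported:

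- **That EOT success is biased towards 100%.** Inflation is possible but not shown. The documents give no resolution rates and no extension rule, and the counts in step 3 are assumptions.
- **That a common-time figure can only be equal or lower.** At Week 6 it can be higher, as the opposite case in step 3 shows.
- **That the type I error in 6.2 is inflated.** The figures in step 5 would apply only if π were the EOT outcome, which 6.2 does not say. No stated error rate is shown to be affected.

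The change is worth making because it is cheap and serves a named secondary objective. It does not bear on the primary safety objective or on the sample size.

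**What to change.** In 12.5, add clinical outcome at Week 4 and at Week 6, counted from enrollment (or first dose) with a stated visit window, for all treated children. Use the 9.5 assessment, or the EOT record when the visits coincide. For this analysis, a child still on antibiotics for unresolved infection counts as not resolved; a child finishing a planned course with a resolved site is judged on the site. Children already classed as failure or indeterminate under 7.8 stay in the denominator and are shown as such. Keep the EOT outcome and report total antibiotic days beside it.

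Also state one starting day for the visits: reconcile the reference to discharge in 9.5 and Table 1.1 with footnote 14. Add the clinical-outcome mark for these visits to Table 1.1, and bring 12.3 into line with 12.5.

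The cost is a few lines of analysis text, one table and a schedule mark. If visits are now booked from discharge, either the booking or the window must be adapted, since by step 4 the same visit can fall up to 10 days apart from the start of treatment (day 33 against day 43 for Week 4). The drawback is a second success figure that may differ from EOT, often lower but at Week 6 possibly higher. Treatment duration is not changed.

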12.6. Interim Analysis

An interim analysis of pharmacokinetics parameters may be performed using data from the first 5 evaluable patients to complete the study. The results of this interim analysis may be used to confirm the planned Ceftaroline dose, or support an appropriate dose adjustment. Enrollment will not be held during the interim PK analysis.

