4.4. Rationale for Ceftaroline Fosamil Dosage Regimen

The selected ceftaroline dose regimens (15 mg/kg [600 mg if > 40 kg] as a 2-hour infusion q8h) are expected to achieve PK/PD targets associated with 1-log kill of *S. aureus* in the murine pneumonia model for organisms with MIC values up to 1 mg/L in > 90% of patients 2 months to < 18 years. The median Cmax value in children 1 year to < 18 years with normal renal function dosed with 15 mg/kg q8h as a 2-hour infusion predicted to be less than the median Cmax value in adults dosed with 600 mg q8h as a 1-hour infusion. The median AUC0-24h in children 1 year to < 18 years dosed with the above regimen is predicted to be up to 15% greater than in adults dosed with 600 mg q8h. The median f T > MIC for an MIC of 1 mg/L is predicted to be 84-93% for the recommended pediatric dose regimens compared to 100% in adults dosed with 600 mg q8h.

Initially, the sponsor believed that a dose of 15 mg/kg q8h to match the dose of 600 mg q8h in adults was appropriate for children from 6 months to <18 years. However, based on findings in the pediatric ABSSI and CABP studies, a lower dose of 10 mg/kg q8h is more appropriate for children from 6 months to < 2 years in order to avoid higher AUC values. The 10 mg/kg q8h dose in this age range is expected to result in a median fT (unbound drug time over MIC) > MIC of 78-88% for an MIC of 1 mg/L and 58-66% for an MIC of 2 mg/L. This would give nearly 100% target attainment for a target of 50% at an MIC of 1 mg/L. The higher dose of 15 mg/kg q8h would still be appropriate for children 2 and older.

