 - Obtain blood sample for Alkaline Phosphatase, Bilirubin, AST and ALT, if clinically indicated.
 - If clinically indicated, estimate CrCl using the updated Schwartz "bedside" formula (Schwartz et al, 2009).
 - Collect results of blood cultures only if conducted per standard of care.

- Collect purulent material from bone only if a procedure is performed for standard of care when possible.
- PK Procedures:
 - Efforts will be made to obtain 1 PK blood sample (approximately 0.6 mL) at steady state from all subjects who received ceftaroline fosamil on Days 2 to 5 of treatment (only one PK sample collected on days 2-5) 4 hours (+/- 30 minutes) after the end of the infusion (before the start of the next infusion). PK samples may be collected after any infusion of ceftaroline fosamil on those days and before oral switch.
 - If purulent material is being obtained from bone or subperiosteal abscesses at surgery or via drainage by interventional radiology, we will attempt to obtain specimens for measurement of ceftaroline concentrations.

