12.7. PK Analysis

The mean and median concentrations of ceftaroline in plasma at the end of infusion will be determined. The proportion of children with plasma ceftaroline concentrations $\geq 1 \mu\text{g/mL}$ at 4 hours after infusion will be determined.

The plasma levels of ceftaroline obtained at 4 hours after the end of a 2 hour infusion will be compared to the ceftaroline MIC for the *S. aureus* isolate recovered causing the osteomyelitis. Ideally, the plasma level should exceed the MIC at this time point which would be for at least 75% of a dosing interval. Assuming the patients do well clinically, there will be no adjustment of the dose even if the target concentration is not achieved at the 6 hour time point following the start of ceftaroline infusion. However, if two subjects do not improve as anticipated, the study will be halted and plasma levels compared to the MICs of the causative *S. aureus* isolates. If plasma levels exceed the MIC and yet the subjects are considered treatment failures in that they are not responded as expected, the investigator would conclude that ceftaroline may not be particularly effective in treating *S. aureus* osteomyelitis in children. If the plasma levels at this time point are below the MIC, a dose modification may be considered but the investigator may decide that studying ceftaroline for this indication is no longer necessary.

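### Sections 12.6 and 12.7 conflict on whether interim PK can change the dose when levels are low but children are doing well; separately, the interim does not distinguish the dose regimens

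*Combined protocol and SAP*

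**What the plan says.** **Interim (Section 12.6).** "An interim analysis of pharmacokinetics parameters may be performed using data from the first 5 evaluable patients to complete the study". On its use: "The results of this interim analysis may be used to confirm the planned Ceftaroline dose, or support an appropriate dose adjustment". And: "Enrollment will not be held during the interim PK analysis". The section gives no concentration threshold, clinical condition, decision-maker or split by regimen. It does not define which patients count as evaluable.

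**Dose rule (Section 12.7).** "Assuming the patients do well clinically, there will be no adjustment of the dose even if the target concentration is not achieved". Then: "However, if two subjects do not improve as anticipated, the study will be halted and plasma levels compared to the MICs". Only after that halt, and only if levels are below the MIC, does the section contemplate a modification. Section 7.10 likewise stops the study at two treatment failures. Sections 12.6 and 12.7 do not refer to each other.

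**Regimens (Section 8.1).** Children aged 1 to under 2 years receive 10 mg/kg. Those aged 2 to 17 receive 15 mg/kg, or 600 mg above 40 kg. Section 4.4 explains that the lower dose under age 2 was chosen "in order to avoid higher AUC values".

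**Sampling (Sections 9.3 and 9.8.3).** Each child gives one plasma sample, 4 hours (within 30 minutes) after an infusion ends: "only one PK sample collected on days 2-5". Section 12.7 nevertheless plans a mean and median concentration at the end of infusion.

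**Enrollment order (Section 6.2).** Two children over 5 years are enrolled before younger ones.

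**The concern.** The interim is the one place where the plan foresees revisiting the dose without first halting the study. If the five children are recovering and their 4-hour levels are low, the team cannot tell from the plan whether a change is open to them. The dose given to later children would depend on which section was followed. Sections 12.4, 12.5 and 12.7 provide no summary by dose received, so the 18-child results could mix doses without showing it.

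A second gap is independent of the first. Section 12.6 speaks of confirming the planned dose as if there were one. The five children may all come from the older age band, and the 10 mg/kg regimen could then be taken as confirmed although no sampled child had received it.

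**Working it through.** **1. The same concentrations feed both sections.** Section 12.7 says that the 4-hour sample corresponds to 75% of the dosing interval. With a 2-hour infusion every 8 hours, (2 + 4)/8 = 0.75, so the figure reproduces. The 30-minute window gives (2 + 3.5)/8 = 0.69 to (2 + 4.5)/8 = 0.81. As this is the only scheduled plasma sample, the interim must rest on the level that Section 12.7 uses.

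**2. The two sections, case by case.**

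| Situation | Section 12.6 | Section 12.7 | Compatible? |
|---|---|---|---|
| Target met, children well | may confirm dose | no adjustment called for | yes |
| Target missed, children well | may support adjustment | no adjustment | **no** |
| Below MIC, two not improving | may support adjustment | halt, then modification may be considered | yes, if any change waits for the halt |
| Unexpectedly high, children well | may support adjustment | silent | no clash, but no rule |

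**3. Chance that no child on 10 mg/kg is among the five.** Let s be the share of children aged 1 to under 2 years among those filling the open places, drawn independently. The documents give no value for s, so a range is assumed. If two of the five are the over-5 sentinel children, the chance is (1 − s)³. If all five places are open, it is (1 − s)⁵.

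| s (assumed) | (1 − s)³ | (1 − s)⁵ |
|---|---|---|
| 5% | 0.857 | 0.774 |
| 1/17 (even spread over ages 1 to 17) | 0.834 | 0.739 |
| 10% | 0.729 | 0.590 |
| 20% | 0.512 | 0.328 |
| 30% | 0.343 | 0.168 |

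**4. How many children a change could reach.** The Summary anticipates 6 subjects a year, so the fifth enrolls at about 5/6 × 12 = 10 months. Follow-up is 12 months after the last dose (Section 9.7) and participation lasts up to 14 months (Section 6.3). If completing the study includes that visit, the fifth child completes at about month 22 to 24. By then 22/12 × 6 = 11 to 24/12 × 6 = 12 are enrolled, leaving 18 − 12 = 6 to 18 − 11 = 7. This assumes that the first five enrolled are the first five evaluable completers.

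**5. What one level can show.** A single 4-hour concentration can be compared with a target or an MIC. It does not by itself give AUC, the quantity behind the lower dose under age 2, and the plan describes no modelling to bridge the gap. The end-of-infusion mean and median in Section 12.7 have no scheduled sample behind them.

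**The case against.** The strongest reply is that Section 12.6 only permits. The interim may or may not be run, and its results may or may not be used. Leaving the dose alone while children do well complies with both sections. A reader might infer that the two sections issue opposite orders that cannot both be followed; the documents do not support that. The clash is a permission in one section against a prohibition in the other, in one case. Section 12.6 also keeps a role for unexpectedly high levels, and continuing enrollment during the analysis does not exclude a later halt under Section 12.7. All of this stands. It does not tell the team that Section 12.7 limits Section 12.6, because neither section says so.

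Three other tempting readings also go too far:

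- **That the sentinel rule fixes two of the five interim places.** It governs enrollment order, whereas the interim takes evaluable completers. A sentinel child can go off study (Section 7.7.1) or lack a PK sample, since Section 9.8.3 promises only efforts to obtain one. Both calculations are therefore shown.
- **That the interim could not reveal over-exposure.** A markedly high 4-hour level would be visible and could raise suspicion. What it would not do by itself is quantify AUC.
- **That the possible absence of a 10 mg/kg child causes the conflict.** It does not. The two gaps are separate, and analysis across regimens is itself inferred from Section 12.6 naming none.

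It is also fair to say that the amendment step already exists: Section 13.6 requires one for protocol changes, and Section 13.2 requires IRB approval first unless subject safety demands otherwise.

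**Conclusion.** The conflict is real but confined to one foreseeable case: the target is missed and the children are doing well. It should be resolved before the interim is run. Under the planned accrual rate, and if completion includes the 12-month visit, a change would reach about 6 to 7 of 18 children, and only if the optional analysis takes place.

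The regimen gap stands separately. For an assumed 5% to 30% of children aged 1 to under 2 years, the chance that the five include none on 10 mg/kg runs from about 86% to 34% with two sentinel children among them, and from about 77% to 17% with all places open. The spread reflects the missing age mix. It supports saying that the regimen may well go unsampled at the interim, and nothing more precise. The sample size in Section 6.2 is unaffected.

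**What to change.** - Reconcile Sections 12.6 and 12.7 into one rule stating whether, when and on whose decision interim PK can lead to a dose change. No view is taken here on which rule or dose is right.
- Define evaluable for the interim.
- Report interim and final PK results by regimen, and state that a regimen with no sampled child is not confirmed by the interim.
- If a change is made through the existing amendment process (Section 13.6), report safety, efficacy and PK by dose received.
- Reconcile the end-of-infusion summary in Section 12.7 with the sampling schedule in Sections 9.3 and 9.8.3.

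The cost is wording and a few table columns; the reporting by regimen needs no added children or samples. The downside is small, purely descriptive subgroups. With an even age spread, the 16 non-sentinel children would include 16 × 1/17 = 0.94 on 10 mg/kg on average, and none with probability (16/17)¹⁶ = 0.38. An empty column would still be informative, because it would show that the regimen was not studied.
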